Over the entire study, a total of 20 SAEs were reported by 19 subjects. Of these 20 SAEs, 12 SAEs were reported by 12 subjects in the core period and nine SAEs were reported by 7 subjects during the extension period. More subjects in the 60 mg/d dose group (10.1%) experienced an SAE compared to the placebo to 30 mg/d (5.8%), placebo to 60 mg/d (3.9%), and 30 mg/d (4.2%) dose groups. Overall the most commonly reported SOCs for the SAEs were in Gastrointestinal Disorders and Injury, Poisoning and Procedural Complications categories. All of the SAEs were considered by the Investigators to be unlikely related or not related to study drug. Eight of the SAEs were considered by the Investigator to be severe or life threatening. No deaths occurred during the study.

A total of 9 subjects discontinued from the study due to a TEAE; two of these subjects had TEAEs that were considered to be treatment-related; hepatic steatosis in the 30 mg/d group and hepatotoxicity in the 60 mg/d group.

The safety of MN-166 from 30 to 80 mg/d has also been evaluated in single and multiple doses up to 14 days has also been evaluated in healthy volunteers and diabetes mellitus Type 1 & 2 patients and chronic pain patients (diabetic neuropathy and complex regional pain syndrome). MN-166 100 mg/d has been evaluated in single and multiple doses for up to 8 days (following 6 days of dose-incremental 40, 60 and 80 mg/d dosing at 2 days each) in healthy volunteers and diabetes mellitus Type 1 and 2 patients. A Phase 1b safety study to evaluate MN-166 in methamphetamine-dependent addicts recently completed enrollment. In this study, subjects received 40 mg/d for 1 week and then 100 mg/d for 1 week. Medication overuse headache (MOH) pain patients are currently being enrolled in a trial with dosing at 80 mg/d for 2 months and opioid addicts at 100 mg/d for 3 weeks in another trial. To date, approximately 450 subjects have been dosed with MN-166.

The Phase 2 RRMS trial results suggest that MN-166 is best positioned for primary neuroprotection in MS subjects (Fox 2010) and the dose-response data from this and other controlled neurological trials suggest that doses ≥ 60 mg/d may be ideal.

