$$[a_{ih} \ b_{ih}]^T \sim \mathcal{N}(\mathbf{0}, \mathbf{G}), [a_h \ b_h \ c_h \ d_h]^T \sim \mathcal{N}(\mathbf{0}, \mathbf{H}), \epsilon_{ij} \sim \mathcal{N}(0, \sigma^2 \mathbf{I}_i), \text{ and } [a_i \ b_i]^T \perp [a_h \ b_h \ c_h \ d_h]^T \perp \epsilon_{ij}.$$

If individual site variance components in \mathbf{H} are negligible, then the associated random effects will be omitted to simplify the model. In the case that all \mathbf{H} components are negligible, we will revert to Equation (1) for the analysis.

Primary Objective #2: To evaluate the safety and tolerability of ibudilast versus placebo.

The main assessment of safety will involve a comparison of treatment-related SAEs across the two treatment groups. This will be assessed in two ways. First, the percentage of subjects who experience any treatment-related SAE in each group will be compared using a chi-square test. Then, the rates of treatment-related SAEs in each group will be compared using a Poisson regression model. We will also assess the values of laboratory assessments over time across the two groups using a LMM. To assess tolerability, the percentage of subjects who complete the entire treatment period will be compared across the two groups using a chi-square test. Appropriate constraints for baseline imbalance will be used in all statistical models.

Major Secondary Objectives: *To evaluate the activity of ibudilast at two years versus placebo, as measured by:*

- (1) *Diffusion tensor imaging (DTI) in descending pyramidal white matter tracts*
- (2) *Magnetization transfer ratio (MTR) imaging in normal-appearing brain tissue*
- (3) *Retinal nerve fiber thickness as measured by optical coherence tomography (OCT)*
- (4) *Cortical atrophy as measured by cortical longitudinal atrophy detection algorithm (CLADA)*

The secondary objectives will be analyzed using a model similar to that described above for the assessment of BPF. An exception is the OCT analysis will require additional random effects for eyes nested within patients. Additional details are provided below. The baseline intercepts will again be constrained to be equal to account for baseline imbalance.

Other Objectives

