7.2.1 Safety

The primary assessment of safety will compare the percentage of subjects in each group with:

- Treatment-emergent adverse events (TEAEs)
- Treatment-emergent serious adverse events (TESAEs)

The main assessment of safety and tolerability will involve a comparison of treatment-related AEs and SAEs across the two treatment groups. First, the percentage of subjects who experience any treatment-related AE in each group will be compared using the following logistic regression model:

$$\text{logit}(Y_i) = \beta_0 + \beta_1 x_{1i} + \beta_2 x_{2i} + \beta_3 x_{3i} + \epsilon_i$$

where

- Y_i represents an indicator of whether or not i^{th} subject had at least one treatment related AE.
- $x_{1i} = 1$ if i^{th} subject was thought to be receiving immunomodulation therapy at randomization (IFN/GA), and 0 if the subject was not thought to be receiving immunomodulation therapy
- $x_{2i} = 1$ if i^{th} subject was thought to have primary progressive MS at randomization, and 0 if the subject was thought to have secondary progressive MS
- $x_{3i} = 1$ if i^{th} subject was randomized to the Ibudilast group, and 0 if the subject was randomized to placebo group
- ϵ_i is random error for the i^{th} subject

To determine if the percentage of subjects having any treatment related AEs differ across treatment group we will test the following hypothesis:

$$H_0: \beta_3 = 0 \text{ vs. } H_A: \beta_3 \neq 0$$

If the null hypothesis is rejected, and $\beta_3 > 0$, we will conclude that Ibudilast was responsible for a significantly greater frequency of treatment-related AEs. Similarly, if $\beta_3 < 0$, we will conclude that Ibudilast was responsible for a significantly lower frequency of treatment-related AEs. In addition to an overall comparison, this hypothesis will be repeated for assessing the percentage of subjects having at least one treatment-related AE within each MedDRA system organ class (SOC). If there are significant differences between groups within any specific SOC, then additional tests will compare differences across groups for specific MedDRA preferred terms in order to further explore the cause of the observed differences.

In addition to the comparison of percentages in the manner described above, the rates of treatment-related AEs in each group will be compared using the following Poisson regression model:

$$\log\left(\frac{Y_i}{T_i}\right) = \beta_0 + \beta_1 x_{1i} + \beta_2 x_{2i} + \beta_3 x_{3i} + \epsilon_i$$

where

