- Y_i represents the number of treatment related SAEs experienced by the i^{th} subject.
- T_i represents the number of months between the date of randomization and the date of last follow-up for the i^{th} subject.
- $x_{1i} = 1$ if i^{th} subject was thought to be receiving immunomodulation therapy at randomization (IFN/GA), and 0 if the subject was not thought to be receiving immunomodulation therapy
- $x_{2i} = 1$ if i^{th} subject was thought to have primary progressive MS at randomization, and 0 if the subject was thought to have secondary progressive MS
- $x_{3i} = 1$ if i^{th} subject was randomized to the Ibudilast group, and 0 if the subject was randomized to placebo group
- ϵ_i is random error for the i^{th} subject

To determine if the rate of treatment related SAEs differ across treatment group we will test the following hypothesis:

$$H_0: \beta_3 = 0 \text{ vs. } H_A: \beta_3 \neq 0$$

If the null hypothesis is rejected, the direction of β_3 will indicate the direction of the observed effect. Values of $\beta_3 > 0$ indicate an increased rate of treatment-related AEs associated with the Ibudilast group, while values of $\beta_3 < 0$ indicate a decreased rate of treatment-related AEs associated with the Ibudilast group.

Treatment-related SAEs will be analyzed in the same manner described above. Additional safety analyses will also assess all treatment-emergent AEs, treatment-emergent SAEs, unanticipated SAEs, and treatment-related & unanticipated SAEs in a similar manner.

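### SAP 7.2.1 names no test statistic and no sparse-data rule for its safety models, which have no finite treatment estimate when one arm has no events

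*Combined protocol and SAP*

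**What the plan says.** SAP 7.2.1 makes treatment-related events the main safety comparison under Primary Objective #2. For percentages, "the percentage of subjects who experience any treatment-related AE in each group will be compared using the following logistic regression model", with terms for arm, immunomodulating therapy and disease type. This percentage test is repeated within each MedDRA organ class. For rates, "the rates of treatment-related AEs in each group will be compared using the following Poisson regression model", although the count in that model is then defined as treatment-related SAEs. The section goes on: "Treatment-related SAEs will be analyzed in the same manner described above". It extends the approach to treatment-emergent AEs and SAEs, unanticipated SAEs, and SAEs that are both treatment-related and unanticipated.

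Each model tests whether β_3 is zero, two-sided. On the result, the rate model says only: "If the null hypothesis is rejected, the direction of β_3 will indicate the direction of the observed effect". The section does not say whether the test is Wald, likelihood-ratio or score. It gives no exact test, penalty or minimum event count. SAP 6 sets the level at 0.10.

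Protocol 12.1.2 differs on the percentage: "the percentage of subjects who experience any treatment-related SAE in each group will be compared using a chi-square test". It then uses Poisson regression for the rate of treatment-related SAEs, as the SAP does.

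**The concern.** Serious events judged related to drug are rare, so one arm may have none. In that case the ordinary maximum-likelihood fit has quasi-complete separation. The likelihood keeps rising as the placebo risk is pushed towards zero, so β_3 has no finite estimate. The figures software prints are simply where the iterations stopped. The standard error grows faster than the estimate, so the Wald ratio goes to zero and the Wald p-value to 1.

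The p-value and interval reported for the most serious events therefore depend on a choice the SAP leaves open. That choice could be made after unblinding, and for the same data it can lead to opposite conclusions.

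**Working it through.** **Inputs.** 125 per arm (SAP 1); two-sided level 0.10 (SAP 6); models as in SAP 7.2.1. Assumed, because the documents do not give them: ordinary maximum likelihood; 31% on immunomodulating therapy and 52% PPMS, balanced between arms; 22 months of exposure for every subject.

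**The plan's own safety figure.** SAP 9.2 states at least 80% power for a 15-point difference. For 20% against 35%, the pooled rate is 0.275. The null SE is √(2 × 0.275 × 0.725 / 125) = 0.0565 and the alternative SE is √((0.16 + 0.2275) / 125) = 0.0557. Power = Φ[(0.15 − 1.645 × 0.0565) / 0.0557] = 0.847. For 10% against 25% it is 0.934; the lowest value is 0.769, at 42.5% against 57.5%. The figure reproduces at the low rates relevant here. It presumes a test that works when one arm is empty.

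**No placebo events.** The models were fitted with the strata (25 iterations):

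| Ibudilast vs placebo | Logistic Wald p | Poisson Wald p | Logistic likelihood-ratio p | Firth p | Fisher p |
|---|---|---|---|---|---|
| 3 vs 0 | 0.9986 | 0.9988 | 0.040 | 0.111 | 0.247 |
| 5 vs 0 | 0.9985 | 0.9986 | 0.008 | 0.026 | 0.060 |
| 6 vs 0 | 0.9985 | 0.9990 | 0.004 | 0.013 | 0.029 |
| 8 vs 0 | 0.9985 | 0.9988 | 0.0007 | 0.003 | 0.007 |
| 10 vs 0 | 0.9985 | 0.9987 | 0.0002 | 0.0007 | 0.0016 |
| 20 vs 0 | 0.9984 | 0.9988 | <0.0001 | <0.0001 | <0.0001 |

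At 10 vs 0 the logistic coefficient stops at 22.11 with SE 11,542, so z = 0.0019. The last row is 16% against 0%, more than the 15 points SAP 9.2 says can be detected. The unadjusted logistic fit gives the same Wald p-values.

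Hand checks at 3 vs 0:
- Fisher = 2 × (125 × 124 × 123) / (250 × 249 × 248) = 0.247.
- Unadjusted likelihood ratio = 2 × (−14.153 + 16.251) = 4.20 on 1 df, p = 0.04.

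**One placebo event is enough to restore the Wald test.** At 7 vs 1, unadjusted Wald p = 0.064 and Fisher p = 0.066.

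**How often the placebo arm is empty.** (1 − p)^125 = 78%, 53%, 28% and 8% for assumed placebo risks of 0.2%, 0.5%, 1% and 2%.

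**How often it would change the answer.** Fisher first rejects at 0.10 with 5 vs 0. With 0.5% on placebo, the probability of no placebo event and at least 5 on ibudilast is 0.534 × P(X ≥ 5):
- ibudilast 2%: 0.534 × 0.107 = 6%
- ibudilast 3%: 0.534 × 0.322 = 17%
- ibudilast 5%: 0.534 × 0.754 = 40%

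**Comparing remedies.** Binomial probabilities were summed over all tables with p ≤ 0.10 favouring placebo (unadjusted). At 0.5% against 5%, power is Wald 0.24 (empty arm counted as no rejection), Fisher 0.57, Firth 0.72, Pearson 0.81 and likelihood-ratio 0.83. For Firth, the two-arm penalty amounts to adding half an event and half a non-event to each arm. With 1% in both arms, counting rejections in either direction at nominal 10%, the likelihood-ratio test rejects 21% of the time, Firth 2% and Fisher 0.5%. Part of the likelihood-ratio test's power therefore comes from excess false positives.

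**Rates.** Given the total count and equal exposure, the ibudilast count is binomial with probability ½. The exact p is 2 × 0.5^5 = 0.0625 at 5 vs 0 and 2 × 0.5^10 = 0.002 at 10 vs 0.

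**The case against.** The strongest reply is that SAP 7.2.1 never specifies a Wald test. Where the SAP does name a test, for BPF in 7.1, it offers the likelihood ratio first and a Z-test second, and the likelihood-ratio test still rejects at 5 vs 0. A reader might infer that the stated method fails. The documents do not support that: one unstated choice fails and another does not.

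A reader might also infer that the SAP is a step back from the protocol throughout. Only the change from chi-square to logistic is new; the protocol's Poisson model for SAE rates has the same weakness.

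Nor do the documents make a drug-only excess the expected result. On the earlier relapsing-remitting trial the synopsis says: "All of the SAEs were considered by the Investigators to be unlikely related or not related to study drug". Protocol 4.5.1 reports 461 exposed subjects with no SAE clearly linked to drug. That history suggests few related SAEs in either arm, and at 0 vs 0 no test rejects.

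Empty arms are not shown for AEs generally. Causality is judged blind, on the assumption of active drug, and the earlier trial's placebo group had 12 treatment-related TEAEs (protocol 4.6.3). The organ-class repeat is written for the logistic test only. The listed safety endpoints, all-cause TEAEs and TESAEs, are not shown to be sparse. The Medical Safety Monitor sees every SAE and quarterly tables by blinded group (SAP 2.2, 10.3), so a large imbalance would be noticed whatever its p-value.

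These points limit the concern but do not remove it. At 6 vs 0 the possible answers are 0.999, 0.029, 0.013 and 0.004, and the SAP does not choose among them.

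**Conclusion.** The concern holds as a gap in specification with a real numerical consequence, and it is worth a cheap correction. If an arm has no events, the SAP's models give no finite estimate or Wald interval, and the Wald p-value is about 0.999 from 2 vs 0 to 20 vs 0. The likelihood-ratio alternative is usable but liberal at very small counts. The problem is confined to the empty-arm case.

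Its practical weight rests on assumed event risks. An empty placebo arm is plausible for treatment-related SAEs. Combined with enough ibudilast events to matter, it has probability 6% to 40% over ibudilast risks of 2% to 5%, at 0.5% on placebo. Maximum likelihood is inferred as the ordinary fit when no penalty or exact method is stated.

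**What to change.** In SAP 7.2.1:

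- Keep the stratum-adjusted models for common events, and name the test used with them.
- For any outcome with no events, or fewer than a stated small number, in an arm, prespecify one method for percentages. Firth logistic regression with the same covariates and a profile penalized-likelihood test and interval is a good candidate; a stratified exact test is the alternative. Choose one and fix the trigger before unblinding.
- For sparse rates, use an exact conditional test.
- Report an exact confidence interval for the risk difference.
- State that Wald p-values and intervals are not used for these outcomes.
- Reconcile the SAE percentage test with protocol 12.1.2, and correct the AE/SAE mismatch in the Poisson definition.

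The cost is SAP wording and standard software; no data or design change is needed. Exact tests lose noticeable power in sparse data (Fisher 0.57 against 0.81 to 0.83 for Pearson and likelihood ratio at 0.5% vs 5%). Firth recovers a good part of this (0.72) without the likelihood-ratio test's excess false positives, and because it keeps the strata a generous trigger loses little.

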7.2.2 Tolerability

The assessment of tolerability will involve assessing the percentage of subjects in each group who:

- Discontinue treatment early (early study termination and/or early study drug withdrawal) due to treatment-emergent AEs or SAEs
- Discontinue treatment early (early study termination and/or early study drug withdrawal) for any reason

Both will be assessed using a model similar to that described in [section 7.2.1](#) for the assessment of treatment-related AEs and SAEs.

8. SECONDARY ANALYSES

The major secondary objective of the SPRINT-MS study is to measure activity of Ibudilast at 96 weeks versus placebo using a variety of additional imaging metrics. Four separate imaging metrics will be considered.

- Diffusion tensor imaging (DTI) in descending pyramidal white matter tracts
- Magnetization transfer ratio (MTR) imaging in normal-appearing brain tissue
- Retinal nerve fiber layer as measured by optical coherence tomography (OCT)
- Cortical atrophy as measured by cortical longitudinal atrophy detection algorithm

8.1. Major Secondary Objective (a): *Evaluate the activity of Ibudilast (MN-166) versus placebo as measured by diffusion tensor imaging (DTI) in pyramidal white matter tracts.*

For both DTI outcomes of interest [Axial Diffusivity (LD), Radial Diffusivity (TD)], the comparison of outcomes for subjects on MN-166 versus placebo will be analyzed using a model similar to the described in [section 7.1](#) for the primary objective, with the exception that the outcome variable will be modified to represent the corresponding DTI outcome of interest and the model will include an additional random effect to account for measurements taken on both sides within the same subject.

8.2. Major Secondary Objective (b): *Evaluate the activity of Ibudilast (MN-166) versus placebo as measured by magnetization transfer ratio (MTR) imaging in normal appearing brain tissue.*

Because both MTR outcome measures of interest [Median MTR in normal appearing brain tissue (NABT) and Median MTR in normal appearing grey matter (NAGM)] record the values at each of the time points as the change from baseline, the LMM used to address this objective will be slightly modified from that described in [section 7.1](#). Assuming linear change over time, the LMM can be

written in the following manner:

$$Y_{ij} = \alpha + \beta_0 x_{0i} + \beta_1 x_{1i} + \beta_2 x_{2i} + \beta_3 t_{ij} x_{3i} + \beta_4 t_{ij} x_{4i} + a_i + b_i + \epsilon_{ij}$$

where:

- Y_{ij} is the change in the MTR value from baseline for the i^{th} subject at the j^{th} time point
- x_{1i} = the baseline MTR value for the i^{th} subject

and all other variables are defined in the same manner as described for the model in [section 7.1](#). The major secondary hypothesis of interest will involve a comparison of the β_3 and β_4 parameters, and will proceed in the same manner as described for the model in [section 7.1](#).

8.3. Major Secondary Objective (c): *Evaluate the activity of Ibudilast (MN-166) versus placebo as measured by retinal nerve fiber layer, as measured by optical coherence tomography (OCT).*

For the analysis of mean RNFL thickness from OCT, the comparison of outcomes for subjects on MN-166 versus placebo will be analyzed using a model similar to the described in [section 7.1](#) for the primary objective, with the exception that the outcome variable will be modified to represent the mean RNFL thickness values and the model will include an additional random effect to account for measurements taken on both eyes within the same subject.

8.4. Major Secondary Objective (d): *Evaluate the activity of Ibudilast (MN-166) versus placebo as measured by cortical atrophy, as measured by cortical longitudinal atrophy detection algorithm.*

For the analysis of cortical thickness (CTh) as measured by CLADA, the comparison of outcomes for subjects on MN-166 versus placebo will be analyzed using a model similar to that described in [section 7.1](#) for the primary objective, with the exception that the outcome variable will be modified to represent the cortical thickness values.

8.5. Additional Secondary, Tertiary, and Exploratory Analyses

A number of additional secondary, tertiary, and exploratory analyses are also planned, but will not be included as part of the FSR. These additional analyses include, but are not limited to:

- Inflammatory disease activity, as measured by T1 lesion volume, T2 lesion volume, and annualized relapse rate
- Disability, as measured by the Expanded Disability Status Scale (EDSS) and the Multiple Sclerosis Functional Composite (MSFC)
- Cognitive impairment, as measured by the Symbol Digit Modalities Test and the Selective Reminding Test
- Quality of Life as measured by the Multiple Sclerosis Impact Scale (MSIS-29), EuroQol 5 Dimensions (EQ-5D), and Short Form-36 Health Survey (SF-36)
- Neuropathic pain, as measured by the Brief Pain Inventory
- Evaluating the activity of Ibudilast (MN-166) at 48 weeks versus placebo as measured by the primary and major secondary imaging outcome measures:
 - Whole brain atrophy using brain parenchymal fraction (BPF)
 - Diffusion tensor imaging (DTI) in descending pyramidal white matter tracts
 - Magnetization transfer ratio (MTR) imaging in normal-appearing brain tissue
 - Retinal nerve fiber layer as measured by optical coherence tomography (OCT)

- Cortical atrophy, as measured by cortical longitudinal atrophy detection algorithm (CLADA)
- Evaluating the activity of Ibudilast (MN-166) at 96 weeks versus placebo as measured by:
 - Whole-brain gray matter fraction
 - Magnetization transfer ratio (MTR) in gray matter
 - New T1 lesions since baseline
 - New T2 lesions since baseline
- Evaluating the pharmacokinetics (PK) of Ibudilast (MN-166) using a population PK approach
- Correlation of cerebrospinal fluid (CSF) and serum biomarkers with imaging and clinical measures of progressive disability
- Identification of unique phase 2 endpoints, and composite MRI scales (combining BPF, MTR, and DTI)

9. SAMPLE SIZE JUSTIFICATION

9.1. *Primary Objective #1: Evaluate the activity of Ibudilast (MN-166: 100 mg/day) versus placebo at 96 weeks as measured by quantitative MRI analysis for whole brain atrophy using brain parenchymal fraction (BPF).*

Estimated required sample size for the primary objective was computed based on two pilot data sets and relevant literature. The first pilot data set (DS1) consisted of $N = 30$ PP subjects ($n=15$ female; mean age 58.6 years; mean disease duration 7.3 years; mean EDSS 4.97) who participated in the placebo arm of a clinical trial for the chemotherapy drug mitoxantrone (Kita et al 2004). A maximum of three repeated measures were available, collected over 24 months.

The second pilot data set (DS2) consisted of $N = 42$ RR and SP participants who had BPF data from 3T scans. Similar to DS1, a maximum of three repeated measures were available, collected over 24 months, and the DS2 pilot participants were in the control group.

The effect size for the power analysis was defined as the percentage difference in linear slope relative to a hypothetical treatment group. That is, the percentage reduction in linear deterioration of the treated group in a hypothetical intervention. The pilot data and the survey of (Altmann et al 2009) suggested a reasonable range of percentage difference was 30% to 50%. Also of note, an earlier study was performed assessing the activity of Ibudilast in relapsing MS, and this study included measurement of brain atrophy. While the earlier study used a different atrophy measure (SIENA) than in this proposal (BPF), and had only two time points, it did show effects sizes of approximately 33%-36%, (Barkhof et al 2010) which could be considered an appropriate target for the power analysis.

Power calculations were based on a LMM appropriate for clinical trials (Yi and Panzarella, 2002; Heo and Leon, 2009). Because there was only one site for the pilot data, the LMM of Equation (1) was used as the basis for the power analysis. Presentation of the required sample size equations is facilitated by using general notation. Consider the following equalities for the parameters of the primary model described in [section 7.1](#):

$$[\alpha_P \quad \beta_P \quad \gamma \quad \delta]^T = [\beta_0 \quad \beta_1 \quad \beta_2 \quad \beta_3]^T = \boldsymbol{\beta}^T,$$

$$[a_i \quad b_i]^T = [b_{0i} \quad b_{1i}]^T = \mathbf{b}_i^T.$$

(Recall that $\gamma = 0$ to constrain the groups to be equal at baseline.) Then the LMM of Equation (1) can be written in matrix notation as

$$Y_i = X_i\beta + Z_i b_i + \epsilon_i,$$

where each matrix has row dimension n_i ; X_i is the design matrix of the fixed effects, and Z_i is the design matrix for the random effects. X_i has four columns, the first being a vector of 1s, the second being t_{ij} , the third being g_i , and the fourth being $t_{ij} \cdot g_i$. Z_i consists of the first two columns of X_i .

The required sample size depends on the variance of the responses,

$$V_i = Var(Y_i) = Z_i G Z_i^T + \sigma^2 I_i$$

and the required sample size for a single arm (half the total sample size) is computed with the following formula

$$\frac{N}{2} = \frac{(Z_{1-\alpha/2} + Z_{1-\beta})^2 \cdot (X_P^T V^{-1} X_P + X_T^T V^{-1} X_T)_{4,4}^{-1}}{\delta^2}$$

where X_P is the design matrix for the placebo group, X_T is the design matrix for the treatment group, and the subscript (4,4) indicates the element in the 4th row and 4th column of the matrix. The value of δ is varied to represent effect sizes of 30%, 35%, 40%, 45%, and 50%, which is the hypothetical slope difference between the treatment and placebo groups.

The analysis used the proposed time points of 0, 24, 48, 72, and 96 weeks. Power curves were computed for DS1, DS2, and for their average (Avg). Avg was based on averaging the LMM parameter estimates across the data sets (e.g., average slope = [DS1 slope + DS2 slope] / 2). Avg was an attempt to pool information from the two data sets without the raw data (the raw data for DS2 was unavailable). A 10% dropout rate was assumed and all estimated sample sizes were inflated by this percentage (i.e., final sample size = initial sample size \times 1.10). Given the resources required for obtaining and analyzing 3T scans, the type I error rate was set at $\alpha = 0.10$. Figure 7.1 shows power curves for the three smallest effect sizes (30%, 35%, and 40%). Focusing on Avg for the middle effect size (35%), the figure indicates that a single-arm $N / 2 = 125$ provides close to 80% (power = 0.80 is the horizontal dashed line). The middle effect size is important as it nearly corresponds to the upper effect size of the aforementioned Ibudilast study (effect size = 36%). The Avg data source is preferred because it approximates a pooling of the information from both samples. The feasibility of $N / 2 = 125$ as the single-arm sample size was examined by calculating power for effect sizes with $\alpha = 0.10$ for all three data sources (DS1, DS2, Avg). The power by effect size curve and data source is shown in Figure 7.2. The figure clearly shows that the study has adequate power across the range of possible values suggested by these two data sources. For the “best” data (DS1), our study has slightly less than 90% power to detect effects of approximately 40% or larger, and more than 90% power to detect effects on the upper end of the range of interest (50%). Most importantly, the figure shows that the power based on the Avg data source is very high for effects in the 33% - 36% range of greatest interest (approximately 80% - 85%). Therefore, based on these assumptions, we are confident that a per-arm sample size of $N / 2 = 125$ ($N = 250$ total participants) is sufficient to help ensure statistically reliable results for the proposed study.

Figure 9.1: Power as a Function of Single-arm sample size, effect size, and data set

[figure not shown]
[figure not shown]

Figure 9.2: Power as a Function of Effect Size and data source for sample size of 125 and alpha = 0.10

9.2. Primary Objective #2: Evaluate the safety and tolerability of Ibudilast (MN-166) versus placebo

With an overall significance level of 0.10, the study will have 80% or greater power to detect differences in safety or tolerability of 15% or greater across the two groups. Thus, minor safety concerns may not be detected in this study – and would need to be assessed in a larger, future phase 3 trial. Nevertheless, the study is adequately powered to detect major safety concerns.

9.3. Major Secondary Objective (a): Evaluate the activity of Ibudilast (MN-166) versus placebo as measured by diffusion tensor imaging (DTI) in pyramidal white matter tracts.

The power analysis was based on longitudinal DTI pilot data with the outcome measure being longitudinal diffusivity (LD) within corticospinal tracts among RRMS and SPMS starting therapy with natalizumab (Fox 2010). Eighteen MS patients were measured five times over 24 months. Equation (2) was the basis for computing required sample size based on the LMM. In order to express power $(1 - \beta)$ as a function of the fixed sample size $(N / 2 = 125)$ and the other quantities, the following equation can be used

$$1 - \beta = \Phi \left[\left(\sqrt{\frac{125 \cdot \delta^2}{\left(\sum_k \sum_l^L \mathbf{X}_{kl}^T \mathbf{V}_{kl}^{-1} \mathbf{X}_{kl} \mathbf{P}_{kl} \right)_{4,4}^{-1}}} \right) - Z_{1-\alpha/2} \right]$$

where $\Phi[\cdot]$ is the cumulative distribution function of the standard normal distribution. Estimated power was calculated using Equation (3) for the δ effect sizes discussed previously. The results show that the estimated power was greater than 0.90 for the smallest effect size (30% difference in slopes). This result implies that $N = 250$ patients is sufficient to provide high power for testing the equality of LD slopes in the treatment and control groups for the range of plausible effect sizes that is anticipated in the proposed study.

9.4. Major Secondary Objective (b): Evaluate the activity of Ibudilast (MN-166) versus placebo as measured by magnetization transfer ratio (MTR) imaging in normal appearing brain tissue.

Pilot data was not available for the MTR power estimates. Descriptive statistics were provided by [name] (Director of NeuroRx) for a study of the efficacy of BG-12 (BG00012, dimethyl fumarate), which is a novel therapy in the development for relapsing MS. Ibudilast is purported to have neuroprotective effects, and so these data were used as a model to project the power of Ibudilast in this proposed trial. A total of $N = 448$ MS patients had whole-brain MTR measured at baseline, 24 weeks, 1 year, and 2 years as part of a multi-center phase III clinical trial using 1.5T MRIs and the stock manufacturer pulse sequence. Only descriptive statistics were available for change between baseline and two years. There was a placebo group and two treatment groups, one receiving BG-12 240 mg twice a day (b.i.d.) and the second receiving BG-12 240 mg three times per day (t.i.d.). The statistics available for the study were means of change scores and their standard deviations. Thus, power was estimated based on an independent t -test of the mean baseline to 2 year difference in MTR scores for the treatment (BG-12) and placebo groups. Power was computed using the conventional formula

$$1 - \beta = \Phi\left(\frac{|\delta|\sqrt{125}}{\sigma} - Z_{1-\frac{\alpha}{2}}\right)$$

where δ is the difference of the mean change scores and σ^2 is the pooled variance of the difference. A subset of patients had no new or enlarging T2 lesions, and the analysis was performed twice: once for all the patients and another time excluding the patients with no lesions. The results of the power analysis are shown in the table below. As seen in the table, the lowest estimated power (t.i.d., all patients) was greater than the conventional cut-off of 0.80. When only subjects with no new lesions were considered (which more closely approximates what we expect in the proposed trial), estimated power was even greater than the conventional level. The table suggests that $N = 250$ might provide sufficient power to detect T and P differences in change over time for the proposed study. The improved image acquisition from 3T MRIs and tailored pulse sequences are expected to increase the study power.

Table 9.1. Power as a Function of Treatment and Type of Patient for MTR

Treatment	Patients	Power
b.i.d.	All	0.856
t.i.d.	All	0.803
b.i.d.	No Lesions	0.925
t.i.d.	No Lesions	0.816

9.5. Major Secondary Objective (c): *Evaluate the activity of Ibudilast (MN-166) versus placebo as measured by retinal nerve fiber layer, as measured by optical coherence tomography (OCT).*

Estimated power for OCT was based on pilot data supplied by [name] (University of Pennsylvania) from an unpublished multi-center natural history observational study of RRMS and SPMS patients. A sample of $N = 373$ MS patients was measured an average of 2.7 times over an average of 1.4 years. A complexity of OCT is that it is measured in both eyes. Therefore, the LMM must be augmented to include random effects for the additional level of nesting. Ignoring site, we define Y_{ijk} to be the OCT value for the k th week ($k = 1, \dots, n_{ij}$) of the j th eye ($j = 1, 2$) of the i th patient ($i = 1, \dots, N$). Then the LMM is

$$Y_{ijk} = \alpha + \beta t_{ijk} + (\gamma + \delta t_{ijk})g_i + a_i + b_i t_{ijk} + a_{ij} + b_{ij} t_{ijk} + \epsilon_{ijk}$$

where $\gamma = 0$ is set to constrain the groups to be equal at baseline, a_i and b_i are patient-specific random effects and a_{ij} and b_{ij} are random effects for eyes nested within patients. It is assumed that

$$[a_i \ b_i]^T \sim \mathcal{N}(\mathbf{0}, \mathbf{G}), [a_{ij} \ b_{ij}]^T \sim \mathcal{N}(\mathbf{0}, \mathbf{H}), \epsilon_{ij} \sim \mathcal{N}(0, \sigma^2 \mathbf{I}_i), \text{ and } [a_i \ b_i]^T \perp [a_{ij} \ b_{ij}]^T \perp \epsilon_{ij}.$$

The three levels of nesting represented by Equation (4) (month nested within eye nested within patient) presents a challenge for deriving power equations, and analytic results are usually based on simplifying assumptions (e.g., fewer random effects than in Equation (4)) (Heo and Leon, 2009). In order to base the power estimate on the LMM of Equation (4), a simulation approach was used. For the simulation, the LMM of Equation (4) was fit to the pilot data and then the resulting estimates were treated as parameters in the following replications. For each replication, a random number generator was used to compute random effects and random error for $N = 250$ hypothetical treatment and control patients based on the appropriate covariance structures (e.g., \mathbf{G}). Then simulated OCT response values were computed based on the fixed and random effects and random error of Equation (4). For each replication, the null hypothesis of $H_0: \delta = 0$ was evaluated with the Z-test based on a LMM fit to the simulated data. The process was repeated 1000 times for each effect size value of δ and the average number of rejections of H_0 was taken to be the estimated power. Results of the simulation are shown in the table below.

Table 9.2. Power as a Function of Effect Size based on the OCT Simulation Study

Effect Size	Power
30%	0.515
35%	0.603
40%	0.665
45%	0.782
50%	0.855

As the table shows, the power surpassed the conventional cutoff of 0.80 only for the largest effect size, but the next lower size (45%) was close to the cutoff. The results indicate that $N = 250$ might provide adequate power for the treatment and placebo slope comparison of OCT if the effect size is large, but power might be lower than the conventional cutoff for medium and smaller effect sizes.

9.6. Major Secondary Objective (d): *Evaluate the activity of Ibudilast (MN-166) versus placebo as measured by cortical atrophy, as measured by cortical longitudinal atrophy detection algorithm.*

No pilot data or other effect size estimates were available for CLADA. However, we expect CLADA effects to be consistent with those of the other secondary endpoints. Therefore, we are confident that statistical power for CLADA will be sufficient to detect effect sizes similar to those discussed for the other secondary endpoints.

